7.4.2 Discontinuations from Study Therapy

Discontinuation from study therapy is defined as subject's termination of the study medication without resumption prior to study completion. Discontinuation from study therapy during the treatment and DB period will be summarized by reason for the premature termination, taken from the study status case report form (CRF) pages. These summaries will be provided based on the MITT analysis population by randomized treatment group and overall.

7.4.3 Treatment Compliance

The CRF for this study will capture information on doses of the study medication. All subjects who skip any study drug dose will be listed. The number of subjects with missed doses (excluding missed doses due to premature discontinuation from the study) by number of missed doses will be summarized based on the As-treated analysis population for the DB period by treatment groups.

7.4.4 Anti-rheumatic Medication

For the purpose of this analysis plan, the term DMARDs will refer to non-biologic DMARDs. Anti-rheumatic medication summaries will be provided to present the medication use of corticosteroids, NSAIDs, and DMARDs. Number and percent of subjects receiving corticosteroids, NSAIDs, and DMARDs will be summarized by treatment group for MITT analysis population during the DB period.

In addition, the mean weekly MTX dose at scheduled visit and mean daily dose of corticosteroids during the DB period will be summarized.

A comprehensive listing of all concomitant medications will be also provided for the MITT analysis population.

7.5 Efficacy

The efficacy analyses will be performed using the efficacy analysis population. The results will be grouped by “as randomized” treatment groups, unless otherwise specified. No formal statistical testing was pre-specified for other efficacy endpoints except the primary endpoint of ACR20 and ACR70 response at Day 85. The analyses of binary endpoints and continuous endpoints will be provided over time including the milestone visits (e.g. Day 85).

Note: If the enrollment is terminated for all treatment arms based on Week 4 interim analysis, the sensitivity analyses, per-protocol analyses, sub-group analyses and additional analyses as defined in the following sections may not be performed based on smaller sample size.

7.5.1 Primary Efficacy Endpoints in Double-blind Period

The co-primary efficacy endpoints are ACR20 and ACR70 response rate at Day 85.

The Chi-square tests will be used to compare the ACR20/70 response rates at Day 85 between each of the active treatment arms and the placebo arm. The Chi-square p-value will be provided for each comparison between the active treatment and the placebo arm. Within each treatment group, the statistical testing will be performed for ACR20 at level of 0.05 first. If it is statistically significant, then the statistical testing will be performed for ACR70. Otherwise, testing will be stopped for this treatment group. All treatment groups will follow the same testing procedure.

In addition, the difference of the response rates between each active treatment and the placebo will be estimated and their corresponding 95% confidence interval will be calculated for Day 85 visit and other applicable visits.

The point estimate for ACR response rate along with 95% confidence interval will be calculated for each treatment arm for each applicable visit.

All subjects who prematurely discontinue the trial after receiving study medication will have missing data imputed as non-responder at all scheduled protocol visits subsequent to the point of discontinuation. The analysis will be preformed based on Efficacy Analysis Population analysis population. More details of imputation rule for classification of binary response status are provided in [Sections 8.3](#).

A sensitivity analysis of statistical testing may be preformed using the Cochram-Mantel-Haenszel(CMH) Chi-square test with stratification factors (prior treatment failure status and region). The CMH Chi-square p-value will be provided for each comparison between the active treatment and the placebo arm along with the relative risk and its 95% CI. Similar testing procedure as the primary analysis will be conducted. The absolute treatment difference and its 95% CI will be provided using the minimum risk Weights⁸. In case in a given stratum, there are 0 responders (all non-responders) in the compared treatment groups, 0.5 will be added to (subtracted from) both treatment groups in order to avoid a variance of 0 in that stratum.

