4.4 Method of Assigning Subject Identification

At the time of the screening visit, immediately after written informed consent is obtained and before performing any study-related procedures, the investigator or coordinator will call into the Interactive Voice Response System (IVRS or IWRS) designated by BMS for assignment of a 5-digit subject number that will be unique across all sites. Enrolled subjects, including those not dosed, will be assigned unique sequential subject numbers by the IVRS system starting with 00001, 00002, 00003, etc. for identification throughout the study. This subject number must not be reused for any other participant in the study.

After completion of all screening evaluations, on Day 1, all eligible subjects will be randomly assigned to 1 of 4 treatment arms (BMS-986142, 100 mg; BMS-986142, 200 mg; BMS-986142, 350 mg; and Placebo) in an equal ratio. To randomize a subject, a phone call will be placed into the randomization option of the IVRS in order to obtain a subject's randomized treatment assignment. Randomization will be assigned in the order in which subjects qualify for treatment, not in the order of study enrollment. The IVRS will be available 24-hours a day, 7 days a week, via a toll-free number. Randomization will be stratified by prior treatment status (MTX-IR vs TNF-IR) and geographic region.

If a subject meets re-screening criteria highlighted in see [Section 3.3.1](#), they must be re-consented, the investigator or coordinator will call into the Interactive Voice Response System (IVRS or IWRS) designated by BMS for assignment of a 5-digit subject number that will be unique across all sites.

Specific instructions (including an enrollment/randomization worksheet) for the central enrollment and randomization procedure using an IVRS will be provided to the site.

Randomized schedules will be generated and kept by the Randomization Group within Drug Supply Management of Bristol-Myers Squibb. The randomization ratio may be adjusted if any dose arm will be discontinued and/or new dose arm will be added based on Week 4 interim analysis.

At all study visits when study drug is dispensed, each subject will be assigned specific container numbers by the IVRS. Container numbers will be assigned non-sequentially and will correspond to the numbers printed on the containers and bottles containing study drug, and will be recorded on the appropriate eCRF.

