- Subgroup analysis of above endpoints by region where applicable (e.g., if any region consists of more than 50% of total subjects and region is classified by North America, Latin America, Europe and Rest of World. One or more regions may be combined for analysis if only limited data in individual region is available).

Descriptive safety analysis:

For the following pre-specified safety endpoints:

- AE/SAE (including but not limited to hypertension, diarrhea, neutropenia)
- Change from baseline in vitals including systolic blood pressure (SBP) and diastolic blood pressure (DBP).

The study will be stopped if intolerable safety events are identified in all treatment arms. If intolerable safety events are identified in 1 or 2 treatment arms, these arms will be dropped and

the study will be continued with caution. New dose levels may be added based on the exposure response analysis (not greater than 350 mg daily). If intolerable safety events show a clear relationship with higher exposure of BMS-986142, a lower dose will be selected where the predicted exposure in ~ 90% of subjects does not exceed the exposure ranges associated with safety findings.

Based on the totality of safety and efficacy considerations, ineffective doses will be stopped at Week 12 and unsafe dose will be stopped immediately.

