The construction of confidence intervals for binary variables will be based on normal approximation, if the number of the events in each individual treatment arm is at least 5. Otherwise, confidence interval using an exact method will be provided. The exact confidence intervals for binary variable within treatment group and between treatment groups will be constructed.

For each of the continuous endpoints, the mixed effect model will be fit with treatment and visit as the fixed effects and measurements within each subject as the repeated measurements. The baseline value will be added into the model as a covariate if necessary. Based on the mixed effect model, the estimate and 95% confidence interval will be calculated for the difference between each active treatment and the placebo at each specified visit.

The results will be presented by treatment groups unless otherwise specified.

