7.3.2 Demography and Baseline Characteristics

Demographic and baseline disease characteristics will be summarized by randomized treatment group and overall based on the MITT analysis populations. For continuous variables, they will be summarized using means, standard deviations and ranges. The distribution of categorical variables such as gender, race etc. will be summarized by treatment group using frequency and percentage.

Demographic characteristics include the following:

- Age in years
- Weight in kgs
- Gender: Male, Female

- Race
- Ethnicity (Hispanic and Non-Hispanic)
- Region grouping scheme A (Latin America+East Europe and ROW) [details in [Appendix 2](#)]
- Region grouping scheme B (North America, Latin America, Europe and ROW) [details in [Appendix 2](#)]
- Stratification (MTX-IR vs. TNF-IR)

Baseline clinical characteristics include the following:

- Duration of disease in years
- Duration of disease (<=2 years, > 2 to 5 years, > 5 years to 10 years, > 10 years)
- ACR functional status classification
- RA classification (2010 ACR/EULAR criteria)
- Individual scores of each ACR components
- DAS28-CRP
- DAS28-ESR
- RF Status: Negative versus Positive
- ACPA Status: Negative versus Positive
- hsCRP (mg/L)
- ESR (mm/hr)
- MTX weekly dose
- Oral daily steroid dose (prednisone equivalents) in mg at Day 1
- Prior non-biologics DMARD therapy: Categorized number of non-biologic DMARDs use prior to randomization (0, 1, 2, >=3)
- Number of subjects with inadequate and/or intolerance to TNFi (overall Yes/No, then categorized by intolerant, no response, insufficient response, and loss of response. Note: subject can be included in more than one category)
- Number of subjects with a primary failure (i.e., insufficient response to the first course of Therapy) (Yes, No)
- Number of subjects with TNFi failures: 0, 1, 2, or >2

7.3.3 *Medical History and Prior Medication*

Medical history and prior medication information before the first study medication will be summarized by treatment group using relative frequencies. Listings of medical history and prior medication will be presented. The results will be based on the MITT analysis population.

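### Randomisation is stratified but the primary ACR20/ACR70 analysis is not: a small efficiency loss for ACR20, with no validity problem and no gain shown for ACR70

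*SAP*

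**What the plan says.** Protocol 4.4 and SAP 2.2 both state: "Randomization will be stratified by prior treatment status (MTX-IR vs TNF-IR) and geographic region".

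The primary comparison uses neither factor. SAP 7.5.1 states "The Chi-square tests will be used to compare the ACR20/70 response rates at Day 85 between each of the active treatment arms" and placebo, with an unadjusted difference in response rates and its 95% interval. SAP 7.1 and Protocol 8.4.2 say the same. Within each dose, ACR20 is tested first at 0.05, and ACR70 only if ACR20 is significant.

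The stratified counterpart is optional: "A sensitivity analysis of statistical testing may be preformed using the Cochram-Mantel-Haenszel(CMH) Chi-square test with stratification factors (prior treatment failure status and region"). It comes with a weighted difference: "The absolute treatment difference and its 95% CI will be provided using the minimum risk" weights. Protocol 8.4.2 contains no stratified analysis. SAP 7.5 adds that, if the Week 4 interim ends enrolment in all arms, "the sensitivity analyses, per-protocol analyses, sub-group analyses and additional analyses as defined in the following sections may not be performed".

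**The concern.** Balancing arms within strata removes part of the chance variation between them. An analysis that ignores the strata still counts that variation in its standard error. If a stratum factor predicts response, the test then runs below its nominal level and loses some power. The question is how much is lost here, and for which endpoint.

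ACR20 matters because it is the gate to ACR70 in every dose group. The method that would recover the loss is already in the SAP, but it has no binding role.

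**Working it through.** **1. The plan's own power.** For n per arm, difference d and mean rate p̄, the stated figures follow the continuity-corrected normal approximation: power = Φ{[d − 1/n − 1.96√(2p̄(1−p̄)/n)] / √[(p0(1−p0)+p1(1−p1))/n]}.
- Protocol ACR20, 33% to 67%, n = 82: (0.34 − 0.0122 − 0.1531)/0.0734 = 2.38, so 99.1% (stated >99%).
- SAP ACR20, 22% to 53%: (0.31 − 0.0122 − 0.1482)/0.0716 = 2.09, so 98.2% (stated 98%).
- ACR70: 90.6% (Protocol, stated ~90%) and 80.4% (SAP, stated ~80%).

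The powers below are for tests without continuity correction, so they are higher for ACR70.

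**2. Is prior treatment prognostic?** Each sample size section gives an overall placebo ACR20 rate and one stratum rate. The other follows if the population bound is taken as exact.
- Protocol 8.1: 33% overall, 40% in MTX-IR, 70:30 mix. TNF-IR = (0.33 − 0.7×0.40)/0.3 = 16.7%.
- SAP 5: 22% overall, 18% in TNF-IR, 20:80 mix. MTX-IR = (0.22 − 0.8×0.18)/0.2 = 38%.
- ACR70: wherever a subgroup placebo rate is given, it equals the overall 2.5%, so no prognostic effect is implied.
- Neither document gives response rates by region.

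**3. ACR20 level with strata balanced.** Level = 2[1 − Φ(1.96/√r)], where r is the within-stratum variance divided by the total variance.
- Protocol: r = (0.7×0.24 + 0.3×0.1389)/0.2211 = 0.2097/0.2211 = 0.948, giving 4.4%.
- SAP: r = (0.2×0.2356 + 0.8×0.1476)/0.1716 = 0.1652/0.1716 = 0.963, giving 4.6%.

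Simulation with permuted blocks (block size assumed, as none is stated) gives 4.4-4.5% and 4.6-4.7%, against 4.9-5.1% for CMH. With no balancing, the chi-square returns to 5.0% at the Protocol rates.

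**4. ACR20 power, 82 per arm, constant difference across strata.** The 15- and 20-point differences are assumptions below plan.

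| Rates | Difference | Chi-square | CMH |
|---|---|---|---|
| Protocol | 15 points | 49.0% | 51.6% |
| Protocol | 20 points | 74.2% | 75.8% |
| Protocol | 34 points (planned) | 99.5% | 99.6% |
| SAP | 15 points | 56.2% | 57.4% |
| SAP | 20 points | 79.6% | 80.5% |
| SAP | 31 points (planned) | 98.8% | 99.0% |

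**5. ACR70 power, placebo 2.5%.**

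| Per arm | Difference | Chi-square | CMH |
|---|---|---|---|
| 82 | 17 points | 96.7-96.8% | 96.8-96.9% |
| 82 | 14 points | 90.6-90.8% | 90.8-91.0% |
| 70 | 17 points | 94.2-94.3% | 93.7-93.9% |
| 70 | 14 points | 86.5-86.6% | 85.1-85.6% |
| 40 | 17 points | 77.1-77.3% | 74.1-74.4% |
| 40 | 14 points | 64.9-65.2% | 61.4-61.5% |

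The ACR70 level at 82 per arm is 4.0-4.1% for both tests. It is low because about 2 placebo responders are expected (82 × 0.025 = 2.05), and stratifying does not change that. The loss at 40 comes from tables at the boundary. For example, 6 against 1 responders of 40 gives a chi-square of 3.91, but a CMH statistic of 3.82-3.83, below 3.84, when the seven responders split 5+2 or 4+3 over the two prior-treatment strata.

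**The case against.** The strongest reply is that nothing is broken. An unstratified chi-square after stratified randomisation is valid, planned power is practically unchanged, and the losses appear only at differences smaller than the sponsor planned. In a Phase 2 trial without multiplicity adjustment this can be called a preference. All of that stands, and it limits the point to one for consideration.

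The stratum rates are also partly derived from bounds read as equalities. The sample size sections do the same: their subgroup sizes of 57 and 65 are about 70% and 80% of 82. The result does move with the mix. At 80% MTX-IR the Protocol inputs give (0.33 − 0.32)/0.2 = 5% in TNF-IR, so r = (0.8×0.24 + 0.2×0.0475)/0.2211 = 0.911 and the level is 4.0%. The direction stays conservative.

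Three stronger readings are tempting and are not supported.
- *CMH should be primary for both endpoints.* ACR70 drives the sample size, gains nothing at 82 per arm and loses power in smaller arms. The synopsis reports that recruitment was stopped early and gives no final size.
- *The waiver in SAP 7.5 has removed the CMH analysis.* It applies only if the Week 4 interim ended enrolment in all arms. The synopsis describes a sponsor decision and does not attribute it to the interim.
- *The region factor is undefined.* SAP 7.3.2 lists two schemes, one being "Region grouping scheme A (Latin America+East Europe and ROW"), and refers to an appendix that is not in the text available here. In Protocol 8.5, "region is classified by North America, Latin America, Europe and Rest of World" describes an interim subgroup analysis and matches the SAP's four-level scheme. SAP 7.5.1 itself does not name the grouping, so naming it there is a clarification.

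**Conclusion.** The concern holds as an efficiency and consistency point for ACR20. The unstratified test runs at about 4.4-4.7% instead of 5.0%. It costs about 1-3 points of power at 15-20 points and under 0.2 points at the planned differences, so the gate to ACR70 is hardly affected if the plan's effect is real. These sizes assume 82 per arm, the partly derived stratum rates and a constant difference across strata. They count prior treatment only, because no region effect can be computed. At 40 per arm with Protocol rates the ACR20 gain shrinks to 0.4-0.6 points.

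A reader might infer inflated type I error or an invalid primary test. Neither follows for the planned concurrent arms, where the departure is on the conservative side. No gain is shown for ACR70.

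**What to change.** In SAP 7.1 and 7.5.1 and Protocol 8.4.2, with the synopsis aligned:
1. **ACR20:** make the CMH test already specified, with a stratified risk difference, the primary analysis. Use the stratification factors and the region grouping of the randomisation system, and name that grouping. Keep the unstratified chi-square as the sensitivity analysis.
2. **ACR70:** keep the unstratified chi-square as primary, and change the CMH sensitivity analysis from *may* to *will*.

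Both should be settled before unblinding. The ACR20-then-ACR70 order within each dose is unchanged.

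The cost is revised wording, slightly more analysis work, and different primary tests for the two co-primary endpoints, which needs a sentence of explanation. Using CMH for both would be tidier and would cost nothing at 82 per arm, but it would give up about 3-4 points of ACR70 power near 40 per arm, more than the ACR20 gain at that size.

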7.5.2 Secondary Efficacy Endpoints in Double-blind Period

For each of the binary endpoints (DAS28-CRP<2.6, CDAI<=2.8 etc.), the estimate and its corresponding 95% confidence interval will be calculated for the difference of the proportions

between each active treatment arm and the placebo arm for each applicable visit, similar to the primary analysis except no p-values will be provided.

For each of the continuous endpoints (DAS28-CRP, CDAI, etc.), the mixed effect model will be fit with treatment and visit as the fixed effects and measurements within each subject as the repeated measurements. The baseline value will be added into the model as a covariate if necessary. Based on the mixed effect model, the estimate and 95% confidence interval will be calculated for the difference between each active treatment and the placebo at each specified visit. No p-values will be provided. In addition, descriptive summary statistics of mean change from baseline and 95% confidence interval for each treatment arm will be provided. The missing data in continuous measures will be handled via utilization of mixed model procedure in SAS.

7.5.2.1 *Magnetic Resonance Imaging (MRI)*

Magnetic resonance imaging will be performed at baseline, Week 4 and Week 12 (or at the time of discontinuation, e.g., early termination visit [ET]). The independent read of MRI image data will be performed by two primary readers who have no knowledge of the subject's identity, treatment arm or time point chronologic sequence. The readers will be presented with the image set(s) of the most clinically swollen hand/wrist acquired at baseline and of that same hand/wrist acquired at Week 4 and Week 12 for the assessment of four parameters of bone erosion, bone marrow edema (osteitis), synovitis, and cartilage loss (joint space narrowing). The scoring of four parameters will be assessed according to the OMERACT RAMRIS criteria⁹.

The MRI score for each parameter is the sum of scores at joints/bone ends where applicable by each reader. The MRI score that is used in the analyses is calculated as the average of MRI scores provided by the two readers for each parameter per each subject at each visit. If a MRI score from one of the readers is missing, then MRI score from the other reader will be used. If the score is missing for both readers at any given time point, the average score is considered missing. If a case requires adjudication, a consensus read of all four parameters will be performed by the two readers working together as defined in the charter. The consensus score will be used in the analysis in this case for each of the four parameters.

If there are more than 20% of joints/bone ends with missing score, the MRI score of each parameter will be considered missing. If there are less than or equal to 20% of joints/bone ends with missing score, the MRI score of each parameter from the missing joints/bone ends will be carried forward from previous scan (e.g., baseline to Week 4, Week 4 to Week 12), or carried backward from later time point or early termination visit (ET) scan if previous scan is not available (e.g., Week 12 to Week 4). If subjects had missing complete MRI assessment at Week 4 or 12, their assessment will be imputed via linear in/extrapolation. Imputation will require a subject to have available scores at minimum 2 visits (including baseline, Week 4, Week 12 or early termination (ET) visit). Subjects with no baseline or only baseline scores will be excluded from the analysis.

The following analyses will be performed based on imputed data unless specified otherwise. In addition, the analysis of changes from baseline may be performed based on as-observed data to assess the robustness of results at the presence of missing data.

The summary of changes from baseline to Week 4 and 12 in each of four parameters will be provided by treatment group using a mixed model. The proportion of subjects with new erosion count (defined as erosion score =0 at baseline and erosion score >0 at post baseline) per hand/wrist will be also summarized at Week 4 and 12.

In addition, the proportion of responders who show no progression of damage based on each of four parameters will be summarized by treatment group at Week 4 and 12 using point estimate and 95% CI, and point estimate and 95% CI of the difference in proportions between the treatment groups. The responder at Week 4 and 12 is defined as the change score from baseline is less than negative value of the smallest detectable change (SDC)¹⁰. The SDC is calculated by $1.96 \times SD_{\Delta(\text{change-scores})}/(\sqrt{2} \times \sqrt{k})$ in which $SD_{\Delta(\text{change-scores})}/\sqrt{2}$ represents the measurement error of single change-scores and k=2 represents the number of readings or raters used for the actual analyses of the trial. The calculation of SDC will be based on the data from two readers excluding the cases that require adjudication.

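### The MRI responder cut-off assumes two readings for every subject, but the SAP lets a single reader's score stand in at any visit, so the cut-off does not fit those subjects

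*SAP*

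**What the plan says.** All of the relevant text is in SAP 7.5.2.1 (Magnetic Resonance Imaging).

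- Default score: "The MRI score that is used in the analyses is calculated as the average of MRI scores provided by the two readers", for each parameter, subject and visit.
- One reader missing: "If a MRI score from one of the readers is missing, then MRI score from the other reader will be used". The rule works visit by visit. It does not ask for the same reader(s) at baseline and follow-up, and change is not formed within reader.
- How a score can go missing: "If there are more than 20% of joints/bone ends with missing score, the MRI score of each parameter will be considered missing". Parameter scores are summed for each reader, so one reader's score can be missing while the other's is present.
- Responder: "The responder at Week 4 and 12 is defined as the change score from baseline is less than negative value of the smallest detectable change".
- Cut-off: SDC = 1.96 × SD_Δ / (√2 × √k), where SD_Δ is the SD of the between-reader difference in change scores and "k=2 represents the number of readings or raters used for the actual analyses of the trial".
- Data behind the SDC: "The calculation of SDC will be based on the data from two readers excluding the cases that require adjudication".
- Robustness: "the analysis of changes from baseline may be performed based on as-observed data to assess the robustness of results". This is optional and names neither single-reader scores nor the responder proportion.

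**The concern.** The divisor √k in the SDC reflects the lower error of an average of k readings. A subject with one reading at one or both visits has a noisier change score than k = 2 implies, so the cut-off is too easy to cross by chance.

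The second mechanism arises only when the set of readers differs between baseline and follow-up. If the two readers score at systematically different levels, a two-reader mean at one visit and a single reader at the other put half of that level difference into the change. The SDC does not allow for this, because a constant level difference cancels out of SD_Δ.

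At stake is whether affected subjects are correctly classed as MRI responders, for four parameters at two visits. The same level shift also enters the mixed model of change scores, which is the listed secondary MRI endpoint (SAP 4.2).

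**Working it through.** The documents state no error rate for the MRI responder analysis, so there is no figure to reproduce. The check is whether the SDC formula keeps its meaning under each pattern of available readers.

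**Inputs.** From SAP 7.5.2.1: the multiplier 1.96, k = 2, response if change < −SDC, and the single-reader rule. Assumed: normal, independent reader errors with SD 1 per reader per visit, equal for both readers and all visits; no true change; a constant level difference b between readers, in units of that SD.

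**Cut-off.** The between-reader difference in change involves four readings, so SD_Δ = √4 = 2. With k = 2, SDC = 1.96 × 2 / (√2 × √2) = 1.96.

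**False response, k = 2 cut-off, no level difference.**

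| Readers behind the change | Error variance of change | False response |
|---|---|---|
| Two at both visits | 0.5 + 0.5 = 1 | Φ(−1.96) = 2.5% |
| Two at one visit, one at the other | 0.5 + 1 = 1.5 | Φ(−1.96/√1.5) = Φ(−1.600) = 5.5% |
| Same single reader at both visits | 1 + 1 = 2 | Φ(−1.96/√2) = Φ(−1.386) = 8.3% |

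The first row shows that the formula is coherent when both readers score both visits. In the third row a level difference cancels and only the extra noise remains.

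**Mixed case with a level difference.** The change shifts by b/2, so false response is Φ((−1.96 ± b/2)/√1.5).

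| b | Shift towards improvement | Shift towards worsening | Mean of the two |
|---|---|---|---|
| 1 | Φ(−1.46/1.225) = 11.7% | Φ(−2.46/1.225) = 2.2% | 6.9% |
| 2 | Φ(−0.96/1.225) = 21.7% | Φ(−2.96/1.225) = 0.8% | 11.2% |

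**No common reader** (one reader at baseline only, the other at follow-up only). The whole difference b enters: Φ((−1.96 ± b)/√2) gives 24.9% or 1.8% at b = 1.

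**With k matched to the readers.** For the same single reader at both visits, k = 1 gives SDC = 1.96 × 2/√2 = 2.77, which is √2 = 1.41 times larger. False response is Φ(−2.77/√2) = 2.5% whatever the value of b.

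A simulation of 1,000,000 subjects agreed with the 2.5%, 5.5% and 8.3%, with the 21.7% and 0.8% at b = 2, and with the 2.5% after matching k.

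**Dilution over an arm.** Rate = 2.5% + f × (rate in affected subjects − 2.5%), with the affected share f assumed to be 5%, 10% or 20%.

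- Mixed, b = 0: 2.6%, 2.8%, 3.1%
- Single reader at both visits: 2.8%, 3.1%, 3.7%
- Mixed, b = 2, shift towards improvement: 3.5%, 4.4%, 6.3%
- Mixed, b = 2, shift towards worsening: 2.4%, 2.3%, 2.2%

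**Continuous change score, mixed case.** Under the SAP rule the mean squared error is 1.5 + (b/2)² = 1.5 + b²/4. Using only the one reader's own change gives 2. The two are equal at b² = 2, so the SAP rule is the more accurate whenever |b| < 1.41.

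**The case against.** **Frequency and size are unknown.** Both readers score the same centrally held images, and protocol 5.4.4.1 has technical failures re-imaged, so many causes of a missing score would affect both readers. The imaging charter and manual are not among the documents and may require complete double reads. This stands: the arm-level effect cannot be established and may be negligible. It does not remove the mismatch, because the SAP itself provides for the single-reader case.

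**k is a trial-level constant, and a subject-specific k gives different thresholds within one proportion.** This is a fair reading of the SAP's definition, and the varying threshold is a real cost. With a fixed k = 2, however, the cut-off does not have the same error meaning for every subject, which is the purpose of an SDC.

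**Within-reader change can be less precise.** This stands for the continuous score, as the mean squared errors show. A reader might infer that the mixed-model analysis should be replaced. The arithmetic does not support that, since the SAP rule is better for level differences below 1.41 SD.

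**Bias between arms.** A reader might infer that the rule inflates MRI response or favours active treatment. The documents do not support this. The level difference can hide response as readily as create it, and the readers are blinded to treatment arm and time order (SAP 7.5.2.1; protocol 5.4.4.1). A shift common to all arms would largely cancel in the contrasts with placebo.

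**Conclusion.** The point holds for the responder classification and is minor. For a subject whose change rests on fewer than two readers at either visit, the k = 2 cut-off is wrong: nominal false response of 2.5% becomes 5.5% to 8.3% from noise alone. In the mixed case it ranges from 0.8% to 21.7% for reader differences up to 2 SD, depending on direction. These figures rest on normal, independent, equal reader errors and on assumed reader differences.

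Two further readings are tempting and go too far. The false-response rates might be taken to apply to the listed secondary endpoint. That endpoint is change in RAMRIS scores, whereas the responder proportion is an additional summary with estimates and confidence intervals, and SAP 7.5 reserves formal testing for the co-primary ACR endpoints, which are unaffected. It might also be supposed that the MRI set is small, so that a few misclassified subjects matter a great deal. The protocol schedules MRI for all subjects (Tables 5.1-1 and 5.1-2) and excludes those who cannot have one (3.3.2). Recruitment was stopped early, but no document describes a small MRI subset.

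**What to change.** In SAP 7.5.2.1:

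1. **Responder classification.** Form the change from the same reader(s) at baseline and follow-up, averaging the readers available at both visits. Set k in the SDC to the number of readers behind that change; k = 1 gives a cut-off 1.41 times larger. Keep the consensus-score rule for adjudicated cases. Treat a subject with no reader common to both visits as not classifiable by SDC. State how the linear in/extrapolation of missing visits fits this, for example by applying it within reader.
2. **Mixed model of change scores.** Keep the current substitution rule as the main analysis. Add a sensitivity analysis using within-reader change or two-reader visits only.
3. **Reporting.** Give the number of single-reader visits by arm and visit, which will show whether the issue mattered and whether missing reads differed between arms.

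The cost is a few sentences in the SAP and minor programming, slightly fewer subjects classed as MRI responders, and a cut-off that depends on the number of readers for what may be only a few subjects. If the imaging charter already guarantees two complete reads at every visit, saying so in the SAP would be enough.
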